A one-year media campaign was conducted in Geneva, Switzerland, using television, radio, newspapers, posters, and leaflets (60). During the first week, hospital visits for chest pain due to cardiac disease increased by 145%, and chest pain due to non-cardiac causes increased by 210% (both significant). At six months, the increases from baseline were 27% for cardiac (p<0.02), and 17% for non-cardiac (NS). Thrombolysis rates increased, but not significantly.

The largest and most well-reported study was conducted in Göteborg, Sweden (61,62). Mass media was used to educate the general population and patients to dial an emergency number to call for an ambulance for chest pain lasting longer than 15 minutes. A three-week intensive media campaign was followed by a maintenance phase of one year, primarily using print materials. A catchy and rhythmic slogan, "Hiarta-Smarta-90000", was used, the primary intent of which was to enable individuals to remember the message and the emergency number. Institution of a special telephone number for dispatch of ambulances for chest pain was combined with the media campaign. For patients with confirmed AMI, median delay time was reduced from three hours to 2 hours-20 minutes, and the distribution of delay times shifted significantly downward. The percentage of AMI patients who received thrombolysis increased, and the estimated infarct size was reduced significantly (63). Although hospital mortality was not affected, the study met other criteria for success, including 66% of the community aware of the campaign, a 6% increase in patients presenting within six hours of symptom onset, and a 9% increase in use of thrombolysis. Infarct size and number of patients developing ventricular fibrillation also were reduced. During the first week of the campaign, there was a marked increase in the number of patients with chest pain arriving at the ED, with the greatest increase observed in those in whom AMI was not suspected; the number of these patients decreased after the first week (62).

2. U.S. Intervention Studies

A two-month public education campaign in Seattle, WA, was carried out in collaboration with the local American Heart Association affiliate (64). The primary messages of the campaign, which used print media and radio and television public service announcements, emphasized the symptoms of AMI, the importance of acting quickly in response to symptoms, and the need to call 911 to activate the EMS

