This group of patients was chosen as the population for the primary analysis for several reasons. First, this group includes those patients who will benefit most from a reduction in delay time by virtue of faster receipt of medical services. Hence, the presence of a reduction in delay should be established in this group, rather than in the larger group of patients that also includes those who have non-cardiac causes of their symptoms. Second, patients with cardiac diagnoses will be more stable across communities and over time than the larger group of patients with symptoms suggestive of acute IHD. Third, patients with cardiac diagnoses will be identified more uniformly and consistently across Field Sites and over the study period. Fourth, sufficient numbers are expected for the purposes of statistical precision and power to adequately examine differences in the primary trial outcomes between intervention as compared to control communities.

A 30-40 minute net reduction in median delay time is considered to be a clinically meaningful intervention effect; thus, in the primary analysis, we will examine delay time as a continuous variable. However, it is also important to increase the percentage of patients who arrive at the hospital within six hours of onset of acute

symptoms, early enough to be treated within the optimal window for receipt of thrombolytic therapy or immediate PTCA. Thus, we will also examine delay time classified as a dichotomous variable (i.e. the proportion of cases delaying < six hours vs $\geq six$ hours).

G. Secondary Outcomes

The following secondary outcomes will be measured and analyzed. The definition and measurement of each outcome is described in Section VII.

- 1. Secondary Populations and Subgroups
- a. The primary intervention effect will be examined among *patients with* diagnosed MI. Since this subgroup includes the vast majority of patients eligible for thrombolytic therapy and/or immediate PTCA, we will examine the intervention effect on their prehospital time delays.
- b. The primary intervention effect will be examined in patients seen in the ED for chest pain and admitted for possible acute ischemia. These patients have been identified by physicians as warranting further diagnosis and/or treatment, and they are targets of the intervention.

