The primary hypothesis will be tested with the conventional Type I error rate of α =5% (two-sided). Sample size estimates are based on a paired *t*-test on the values of *d*, or, equivalently, using a mixed-model ANOVA with REACT group as a fixed effect (1 df). Using the *t*-test formulation, the smallest effect detectable with a specified level of power Π is given approximately by

$$\Delta\beta = SE(\overline{d})(t_{\alpha/2} + t_{1-\Pi}),$$

where t_0 demarks the specified upper tail area of the central Student distribution. The degrees of freedom for *t* are *J*-1=9.

The net end-trial effect on delay time is related to slope as follows. After L=1.5 yr of intervention, the difference in mean log delay time between Intervention and Control communities will be $\Delta y = L\Delta\beta$. The corresponding effect on the median delay time will be a multiplicative reduction by a factor of $10^{-L\Delta\beta}$, or

Relative reduction = $100\% \times (1 - 10^{-L\Delta\beta})$, Absolute reduction = $M \times (1 - 10^{-L\Delta\beta})$,

where M is the median delay time at the end of the trial in the Control communities.

C. Results and Sensitivity Analysis

Detectable effects for the primary endpoint in the primary population are shown in Table 5. Three sample sizes are considered: K=800, 600, or 400 complete, usable cases per community. The figure of 600 represents a conservative estimate, based on the above event rates and attrition parameters. For comparison, a "pessimistic" figure of 400 is included, representing the worst-case parameters with an additional 100 cases subtracted for unforeseen attrition. The "optimistic" figure of 800 per community is probably not attainable but has been included as a benchmark for comparison.

In the conservative case (600 per community), which should be easily attained with the broadened eligibility criteria, the detectable absolute reduction is between 27 and 30 min. if the initial median delay is assumed to be 2.5 hr, as much of the available data suggests. If the initial median is taken as 3.0 hr., the absolute level lies between 32 and 35 min.

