REACT will follow the pattern employed in the analysis of the Minnesota Heart Health Program risk factor and morbidity and mortality data (97), and adapted for the joint analysis of data from the three major U.S. trials of community heart health promotion in the 1980's (71). Pre-intervention data from all 20 communities will be combined with postintervention data from the comparison communities to model a single secular trend. The intervention effect will then be estimated as a departure from that secular trend.

7. Subgroup analyses

Subgroup analyses are often desirable to provide insight into how and for whom an intervention achieved its effect. REACT plans a number of subgroup analyses, all secondary to the primary analyses. These include assessment of the treatment effect on delay among subgroups defined by sex, ethnicity/race, age, history of previous CHD, risk status, and other variables listed in Section IV. These analyses will be patterned after the primary analyses, with appropriate caution added to their interpretation.

8. Inferential parameters

All primary and secondary analyses will employ two-tailed tests with a nominal Type I error rate of 5%.

9. Intention to treat

A commonly followed principle in rigorously evaluated trials is the intention-totreat principle, which states that participants allocated to each condition must be retained in the primary analyses, even if that requires conservative procedures to estimate data for subjects lost to followup. REACT will be relatively protected in this regard, as it is not based on a cohort design and so will not be subject to the usual loss to followup problems. At the community level, the intention-to-treat principal implies that a community must be analyzed as belonging to the treatment condition to which it was randomized, regardless of how well the intervention was implemented (in the case of an intervention community) or how much the community may have been influenced by independent REACT-like messages (in the case of a control community).

B. Analytic Methods

1. Analysis of delay time in the primary population

The primary population for whom delay times in each community will be assessed consists of all patients with confirmed MI or unstable angina. This group will be referred to as *primary patients*. For the primary endpoint, delay time is defined to be the time between onset of symptoms and arrival at the hospital.

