At the individual level, if all sites are pooled, subsampling skews the ethnic composition of the overall REACT sample to some degree. These effects are detailed in Table 7. It should be emphasized, however, that a valid random subsampling scheme would not alter the ethnic balance of the sample collected in any given community. Since all primary and secondary REACT analyses, in keeping with the community randomization design, are planned at the community level, these would not be biased by subsampling.

B. Detectable effect, primary analysis

Sample size is essentially fixed in advance at both levels of REACT, on the community level at 10 pairs and at the individual level by the available number of cases or some convenient sampling fraction. The effect of the REACT Intervention in reducing delay time is by contrast difficult to predict, because comparable interventions have not previously been conducted. As a consequence, power calculations for REACT are most informatively framed with sample size, power, Type I error, and variance as fixed parameters (or, in sensitivity analysis, as independent variables) and detectable effect as the dependent variable. The requisite formulas are derived in this section. The results are tabulated and discussed in

Version 07/01/96

Section E. The sources and choices of operating parameters that enter into the formulas are detailed along with the mathematical derivation. A parameter summary is provided in Table 8.

The primary REACT endpoint is T, the delay time between onset of acute symptoms and arrival at the hospital. Because the distribution of T is skewed according to all reports from previous studies, the primary endpoint for analysis will be $y = \log_{10} T$. All other factors being equal, y will be assumed to have a normal distribution with mean μ and variance σ^2 . Thus T is log-normally distributed with median $M = 10^{\mu}$. In the log-normal distribution, approximately 95% of cases fall within a multiplicative range of $10^{\mu\pm 2\sigma}$. The multiplicative factor $R = 10^{2\sigma}$, according to pertinent data (Section II), is approximately 9. That is, 95% of delay times fall between 1/9 of the median value and 9 times the median value (Figure 7).

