$$SE^{2}(\overline{d}) = V(\overline{d}) = \frac{2\sigma_{\beta}^{2}}{J}(1-\rho) + \frac{\sigma^{2}}{V_{t}J^{2}}\sum_{j=1}^{J} \left[K_{j,Intervention}^{-1} + K_{j,Control}^{-1}\right].$$

The primary null hypothesis of the REACT trial is that the true mean difference between Intervention and Control slopes, $\Delta\beta = \langle \beta_{Intervention} \rangle - \langle \beta_{Control} \rangle$, is zero. The

alternative hypothesis is that $\Delta\beta \neq 0$; this is a two-sided alternative because it is conceivable (though not likely) that the REACT Intervention could prolong the average delay time.

The primary hypothesis will be tested with the conventional critical value (Type I error rate) of $\alpha=5\%$ (two-sided), using a paired *t*-test on the values of *d*, or, equivalently, using a mixed-model ANOVA with REACT group as a fixed effect (1 df). Using the *t*-test formulation, the smallest effect detectable with a specified level of power Π is given approximately by

$$\Delta\beta = SE(\overline{d})(t_{\alpha/2} + t_{1-\Pi}),$$

where t_0 demarks the specified upper tail area of the central Student distribution. The degrees of freedom for t are J-1=9. (In the equivalent ANOVA formulation, denominator df for the Intervention effect are [Communities - (Treatment Groups-1) - (Sites-1) - Sites \times (Pairs per site-1) - 1] = 20 - 1 - 4 - 5 $\times 1 - 1 = 9$.)

Power has been fixed at Π =80% for the primary analysis on the premise that a largescale trial can afford no more than 1 chance in 5 of achieving a result and then failing, because of random chance alone, to prove its success to the scientific community. For secondary populations and endpoints, the calculations have likewise been performed at 80% power.

It is desirable to address the detectable effect on delay time directly, rather than indirectly through the detectable slope difference. Slope is related to the net end-trial effect on delay time as follows. After L=1.5 yr of intervention, the difference in mean log delay time between Intervention and Control communities will be $\Delta y = L\Delta\beta$. The corresponding effect on the median delay time will be a multiplicative reduction by a factor of $10^{-L\Delta\beta}$, or

Relative reduction = $100\% \times (1 - 10^{-L\Delta\beta})$,

Absolute reduction = $M \times (1 - 10^{-L\Delta\beta})$,

where M is the median delay time at the end of the trial in the Control communities.

C. Detectable Effect, Secondary Populations

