In summary, Tables 9-11 suggest that the REACT study as designed has good power to demonstrate a significant primary outcome effect in major subgroups, as well as significant secondary outcomes if their initial prevalence is not extremely high or low. Power is probably not adequate to demonstrate differences between complementary subgroups in the magnitude of the REACT effect. In this Appendix the details of sample size, statistical power, and magnitude of detectable effects will be addressed within a comprehensive theoretical framework, closely linked to the Analysis Plan. In Section A two schemes of subsampling are examined and evaluated as to their impact on statistical power and their potential for skewing the ethnic composition of the REACT sample.

The theoretical basis for the power calculation is developed in Section B, in regard to the primary analysis. Parameter values and mathematical assumptions that go into the model are detailed and documented in greater detail than was provided in Section X.B. In Section C, the theory is extended to cover detectable effects in secondary populations (subgroups or supergroups of the primary population), and in Section D it is extended to cover binary endpoints in the primary population, which comprise many of the secondary endpoints of interest.

The results of the detectable effect calculation for the primary analysis were presented in Section X.C. The analogous results for secondary analyses are presented in Section E, with a discussion of sensitivity to key parameters.

A. Subsampling and Minority Representation

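### Appendix C makes good power for secondary outcomes depend on prevalence alone; for arrival within six hours, power at the trial's own 30-40 minute target runs from about 43% to 90%

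*Protocol*

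**What the plan says.** Section IV.F sets the target: "A 30-40 minute net reduction in median delay time is considered to be" clinically meaningful. It then adds that "it is also important to increase the percentage of patients who arrive at the hospital within six hours" and plans a split of delay time at six hours. Section XI.A.5 lists the six-hour proportion among the important outcomes, and Section XI.B.2.c plans its analysis: a logit slope in each community, then a two-tailed paired t-test over the ten pairs.

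Appendix C.B fixes the delay model: "95% of delay times fall between 1/9 of the median value and 9 times the median value". It gives the detectable effect as the standard error times a sum of Student t quantiles on 9 df, and says: "For secondary populations and endpoints, the calculations have likewise been performed at 80% power". Appendix C.D carries the method over to binary outcomes. Table 11 then lists the odds ratio detectable with 80% power by prevalence. At 600 cases per community the best and worst variance cases are 1.37/1.39 at 50%, 1.41/1.43 at 30 or 70%, and 1.48/1.50 at 20 or 80%.

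The summary at the end of Appendix C.E concludes from Tables 9-11 that power is good in major subgroups, "as well as significant secondary outcomes if their initial prevalence is not extremely high or low".

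**The concern.** Power is a property of a test at a stated effect. Table 11 shows which odds ratios could be detected. Whether power is good depends on how those compare with what the intervention is expected to do, and the protocol makes no such comparison for any binary outcome. A moderate prevalence does not settle the question.

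For six-hour arrival the comparison needs nothing from outside, because the target reduction, the two assumed medians and the spread of delay times are all stated. The outcome also carries weight, since Section IV.F ties six hours to the treatment window. At stake is what a reader believes the design can show on that outcome: a significant primary result beside a non-significant six-hour result would be quite likely at a true 30-minute effect, and the summary gives no hint of this.

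**Working it through.** **Inputs.** J = 10 pairs, 9 df, K = 600, L = 1.5 yr, V_t = 0.237 yr² (Appendix C.B, C.E). Slope variability and pair correlation: R_β = 1.05 with ρ = 0.4 (best case), 1.15 with ρ = 0 (worst case). R = 9, so σ = log10(9)/2 = 0.477. Control median M = 2.5 or 3 h (Section X.C). Two-sided α = 5%.

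**Formula (Appendix C.B and C.D).** With equal K, SE² = 2σ_β²(1−ρ)/J + 2/[π(1−π)·K·V_t·J], where σ_β = ln(R_β)/(2L). The detectable OR is exp(L·SE·q), where q is the sum of the two quantiles.

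**Reproducing Table 11 (50%, best case).** σ_β = ln(1.05)/3 = 0.0163. SE² = 2(0.0163²)(0.6)/10 + 2(4)/(600 × 0.237 × 10) = 0.00003 + 0.00562, so SE = 0.0752.
- Normal quantiles, q = 1.960 + 0.842 = 2.80: OR = exp(1.5 × 0.0752 × 2.80) = 1.37, as printed.
- Prescribed t on 9 df, q = 2.262 + 0.883 = 3.146: OR = 1.43.

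The other K = 600 rows behave the same way. Table 5, by contrast, reproduces with the t quantiles. With t, the K = 600 rows of Table 11 would read (best/worst):

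| Prevalence | Printed | t on 9 df |
|---|---|---|
| 50% | 1.37/1.39 | 1.43/1.44 |
| 30 or 70% | 1.41/1.43 | 1.47/1.49 |
| 20 or 80% | 1.48/1.50 | 1.56/1.57 |

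Two odds ratios elsewhere in Table 11 do not reproduce: K = 400 at 5% prints 2.48 (computed 2.42), and K = 200 at 10% prints 2.42 (computed 2.48). They look transposed.

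**Effect implied for six-hour arrival.** The proportion is p = Φ[log10(6/M)/0.477].
- M = 2.5 h: log10(2.4)/0.477 = 0.797, so p = 0.787. After 30 min (median 2.0 h) p = 0.841, OR 1.43. After 40 min p = 0.860, OR 1.66.
- M = 3 h: log10(2)/0.477 = 0.631, so p = 0.736. After 30 min p = 0.787, OR 1.33. After 40 min p = 0.805, OR 1.48.

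**Detectable OR at these starting prevalences.** About 1.47-1.48 (M = 2.5 h) and 1.43-1.45 (M = 3 h) with normal quantiles; about 1.54-1.56 and 1.50-1.51 with t. The 30-minute effect falls short on either basis.

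**Power.** The noncentrality is ln(OR)/(L·SE). For M = 2.5 h, 30 min, best case: SE² = 0.00003 + 2(5.97)/1422.5 = 0.00842, SE = 0.0918, and 0.360/(1.5 × 0.0918) = 2.61, against the 3.146 needed for 80%. Formula ranges below cover both variance cases, π taken at the start or averaged, and the shifted central t or the noncentral t. The simulation used log-normal delays, a logistic slope per community and the paired t-test, with 1,000 trials per cell.

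| M | Reduction | OR | Formula | Simulation |
|---|---|---|---|---|
| 2.5 h | 30 min | 1.43 | 57-64% | 56-62% |
| 2.5 h | 40 min | 1.66 | 85-90% | 82-85% |
| 3 h | 30 min | 1.33 | 43-51% | 45-48% |
| 3 h | 40 min | 1.48 | 72-78% | 73-76% |

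A second simulation, with 1,500 trials per cell, agreed within a few points; its lowest value for M = 3 h and 40 min was 70%.

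**Reduction needed for 80% power.** About 35-37 min at M = 2.5 h and 41-43 min at M = 3 h.

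**Sensitivity.** With the 750 usable cases per community expected in Section X.A, 30-minute power is 67-74% and 52-60%. With a four-hour cut at K = 600 it is 65-71% and 49-55%. The primary log-delay test on the same 30-minute effect has about 82-89% and 64-74%.

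**The case against.** Several points on the other side stand.

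- Thirty minutes is only the lower end of the target. At 40 minutes power is adequate for M = 2.5 h and modestly short for M = 3 h.
- By Table 11's printed method the reduction needed is about 32-33 min at M = 2.5 h and 37-38 min at M = 3 h. Both lie inside the target range. It is the prescribed t quantiles that push the 3 h figure just beyond it.
- Appendix C.E and Table 11 do print detectable effects, and Appendix C.B explains why effect size is treated as the unknown. Only the summary sentence rests on prevalence.
- The same sentence calls power good for major subgroups, yet Table 9 needs 36-38 min (2.5 h) and 43-46 min (3 h) in a 50% subgroup. Six-hour arrival is no worse. This shows that the word is used loosely in both halves; it does not show that prevalence settles power.
- At M = 3 h the primary test is also short at 30 minutes, and Section X.C discloses a detectable effect of 32-35 min there.

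A reader might infer that the trial is underpowered for its secondary outcomes generally. The documents do not support that. Appendix C.D's examples are thrombolytic therapy and use of 911, for which no expected effect can be derived from the protocol. A reader might also infer that the investigators would treat a null six-hour result as absence of effect; nothing in the protocol says so.

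**Conclusion.** The summary claims more than the tables behind it can support. Six-hour arrival meets its only condition, a prevalence that is not extreme, yet power there is about 57-64% (30 min) to 82-90% (40 min) at a 2.5 h median, and about 43-51% to 70-78% at 3 h. Power reaches 80% only in the upper part of the target range at 2.5 h and just above its top at 3 h. Part of the favourable impression is a separate computational slip: Table 11 does not use the t quantiles that Appendix C prescribes.

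These figures assume log-normal delay with R = 9, 600 usable cases in every community, no secular trend, a linear logit slope, and slope variability within the protocol's own best and worst cases. The primary analysis is unaffected. This is a stated property of the design that needs correcting, not a flaw in the design.

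**What to change.** 1. Recompute Table 11 with t on 9 df, as Appendix C.B and C.D specify, and correct the two odds ratios that look transposed.
2. Print beside it the odds ratios that a 30-40 minute reduction implies for six-hour arrival: 1.43-1.66 at a 2.5 h median and 1.33-1.48 at 3 h.
3. Restate the secondary-outcome half of the summary with the power for this outcome at both medians and both ends of the target, and make no general claim for other binary outcomes.
4. State the cut-point. Section XI.B.2.c splits delay at six hours but then models arrival within four, and the two must be reconciled before the figures are printed. A four-hour cut gives about 49-71% at 30 minutes.

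A sentence saying that a non-significant six-hour result will be reported with its confidence interval, and not read as no effect, would be useful but is optional.

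The cost is wording and one recomputed table. A stated property becomes less favourable; no patients, data collection or procedures change.
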